- n. Serum chemistries (non-fasting), including BUN (urea where BUN not tested), total cholesterol, creatinine, glucose, LDH, , sodium, potassium, calcium, chloride, bicarbonate, magnesium, phosphorus, albumin, and total protein. For intra-patient dose escalation, if Day 1 of the new dose falls on the same day (±3 days) of a previous serum chemistry assessment (e.g., Day 1 of C2 and beyond), it is not necessary to repeat. Patients found to have treatment-emergent laboratory toxicity of Grades 3 or 4 will be monitored at least weekly until resolution.
- o. LFTs, including ALT, AST, alkaline phosphatase, and total and direct bilirubin. For intra-patient dose escalation, if Day 1 of the new dose falls on the same day (±3 days) of a previous liver function assessment (e.g., Day 1 of C2 and beyond), it is not necessary to repeat. Patients found to have treatment-emergent laboratory toxicity of Grades 3 or 4 will be monitored at least weekly until resolution. Increased LFT monitoring should be conducted following dose resumption and any dose re-escalation after toxicity (refer to Section 6 of the selpercatinib IB, Summary of Data and Guidance for the Investigator).
- p. Thyroid-stimulating hormone (TSH), free triiodothyronine (T3), and free thyroxine (T4).
- q. Complete urinalysis, including color, appearance, specific gravity, pH, glucose, ketones, occult blood, protein, leukocytes, nitrites. Beyond Cycle C1D15, urinalysis is only required if clinically indicated.
- r. Calcitonin and CEA only for patients with a diagnosis of MTC. These should be performed in the same laboratory to minimize intra-patient, lab-to-lab variability in their measurement.
- s. Thyroglobulin only for patients with non-MTC thyroid cancers (unless not measurable due to the presence of anti-thyroglobulin antibodies). These should be performed in the same laboratory to minimize intra-patient, lab-to-lab variability in their measurement.
- t. Optional for patients with Cushing's disease related to their cancer. If performed, urine collection should begin pre-dose.
- u. Whole blood for cfDNA analysis should be obtained at C1D1 (pre-dose), C1D15 and C2D1. Whole blood for cfDNA analysis should be obtained at the EOT visit, even if radiologic disease assessment is not performed. If oligometastatic disease constituting progression is identified, but the patient is otherwise stable and will continue selpercatinib beyond progression, patients should have blood collected for cfDNA analysis.

- v. Baseline disease assessment with radiographic tumor measurements using CT or MRI of chest, abdomen, and pelvis or any other areas with suspected disease involvement within 28 days of C1D1. During Phase 2, brain imaging is required at baseline for all RET fusion-positive patients, patients with a history of CNS metastases, or other patients if clinically indicated and subsequent serial scans if brain metastases are present at baseline (MRI preferred, CT with contrast is acceptable if MRI contraindicated). For each modality, IV and oral contrast should be utilized (chest CT does not require IV contrast) unless there is a clear contraindication (e.g., decreased renal function or allergy that cannot be addressed with standard prophylactic treatments). In the absence of known or suspected disease involvement, head and neck CT/MRI scans are not required for malignancies other than those originating in the head and neck region. Other areas of scanning may also differ depending on disease type. Post-baseline scans should be performed every 8 weeks ( $\pm 7$  days) for one year and every 12 weeks ( $\pm 7$  days) thereafter, including imaging of the chest, abdomen, and pelvis, using the same modality(ies) as used for baseline imaging assessment until PD, withdrawal of consent, or initiation of a new anticancer therapy(ies). Additionally, any studies performed at baseline that are positive for sites of disease should be repeated at all post-baseline assessments. Additional studies can also be performed as clinically indicated. In addition, Investigators may conduct an initial tumor evaluation on C2D1 ( $\pm 7$  days) and a confirmatory tumor evaluation a minimum of 4 weeks (i.e., 28 days) after the first tumor evaluation that shows a CR or PR by RECIST 1.1 (or RANO, as appropriate to tumor type), if consistent with local regulatory authority requirements. In addition, an initial post baseline assessment on C2D1 ( $\pm 7$  days) is encouraged if consistent with regulatory guidelines. If a scan is performed on C2D1, the next scan should continue according to the schedule above (beginning at C3D1). All scans will be collected and stored at a central facility to permit central reviewer assessment if desired. Please see the Site Imaging Manual for guidelines on how the various imaging studies should be performed.
- w. If not performed within the last 8 weeks.
- x. Patients who discontinue study drug for reasons other than PD (e.g., AE, noncompliance, etc.) may (but for practical reasons and to minimize patient inconvenience, are not required to) undergo additional disease assessment by imaging (as specified above until PD, withdrawal of consent or initiation of a new anticancer therapy[ies]).
- y. Confirmatory scans: Minimum of 4 weeks (e.g., 28 days) after the first tumor evaluation showing a CR or PR by RECIST 1.1 or RANO, as appropriate to tumor type, if permitted by regulatory authorities. The next scan should continue according to the schedule above.
- z. Study sites will conduct a telemedicine visit when no in-clinic visit occurs to confirm whether the patient is experiencing any new, or changes to existing, AEs/SAEs and concomitant medications, and to confirm study drug compliance and missed doses.
- aa. Up to 1-hour pre-dose, and post-dose 1, 2, and 4 hours ( $\pm 15$  minutes) and 8 hours ( $\pm 30$  minutes). For intra-patient dose escalation, PK samples should be collected pre-dose (up to 1 hour prior to dosing) and post-dose at 1, 2, and 4 hours ( $\pm 15$  minutes) and 8 hours ( $\pm 30$  minutes) on Day 8 ( $\pm 3$  days) of the patient's new dose.
- bb. EORTC QLQ-C30 (patients 18 years and older) and PedsQL (patients age 12-17 years). The questionnaires should be answered by the subject to the best of his/her ability, prior to receiving drug on C1D1 and preferably prior to learning the results of the radiologic disease assessment for subsequent cycles.
- cc. Only for patients with a diagnosis of MTC and diarrhea at baseline. For Cycle 7 and beyond, the patient should personally maintain bowel diary and discuss the diary with the site during telemedicine visits. The bowel diaries should be returned at the next in-clinic visit or provided to study site electronically.
- dd. AEs and SAEs should be recorded from the time that written informed consent has been obtained through the SFU Visit.
- ee. Concomitant, ongoing medication(s) plus those administered within 14 days prior to the planned start of treatment.
- ff. Patients will be followed for survival status, date of progression, and subsequent anticancer therapy(ies) by telephone or other method.
- gg. This is required for adolescents who have not reached adult height (see Section 7.8.6).

**Table 7-2 Continued Access Schedule of Assessments**

Visit	Study Treatment	SFU a	LTFU	Instructions
Procedure b				
Adverse events	X	X		Collect throughout the study.
Selpercatinib administration	X			
Survival	X		X	MTC patients ONLY. Patients who discontinue treatment and 30-day follow up will be followed for survival until End of Study
Progression Date and Type	X	X	X	Only for MTC patients who have not had radiographic progression. Type = radiographic or clinical

- Safety Follow-Up (SFU): 28 days (+7 days) after final dose of study drug.
- Clinic visits during continued access should continue at a minimum of every  $84 \pm 7$  days for IP dispensing. Additional visits may be performed as clinically indicated.

## 7.1 Screening Period

The following must be obtained within 28 days of C1D1 unless otherwise noted. Patients who cannot complete the procedures within the screening window may be rescreened, and certain screening procedures may not need to be repeated, including certain procedures that were obtained as part of the patient's standard care prior to providing informed consent for this study (provided the patient provides informed consent), with the approval of the Sponsor. Screening tests that are completed in the 48 hours prior to start of study drug administration and that duplicate C1D1 tests according to the Schedule of Assessments ([Table 7-1](#)) will be accepted as fulfilling the C1D1 assessments; repeat testing on C1D1 is not necessary for this scenario, and results should be recorded in the Screening set of eCRFs.

- Informed Consent.
- Medical, surgical, and malignancy history, including histologic confirmation of solid tumor, primary and metastatic diagnosis dates, prior treatments for the malignancy, etc.
- Submission of anonymized/redacted Molecular Pathology Report(s) describing RET and other alterations to Sponsor or designee.
- Confirmation of availability of archived tumor tissue to be submitted, either tumor block (preferred) or  $\sim 25 \times 5$  um unstained slides. If archived tumor tissue is not available or is of insufficient quantity or quality, a fresh tumor biopsy should be obtained prior to selpercatinib. If in the opinion of the Investigator, a fresh biopsy cannot be safely performed, the patient may still be eligible with prior Sponsor approval.
- Physical examination, including relevant review of systems, body weight and height, and ECOG performance status or Lansky Performance Score (refer to [Appendix F](#)).
- Vital signs, including systolic and diastolic blood pressure, heart rate, respiratory rate, and body temperature.
- Resting 12-lead ECG.
- Serum pregnancy test for women of childbearing potential (surgically sterilized females or those who have not experienced menses for at least 2 years are not required to be tested).
- Hematology, including hemoglobin, hematocrit, RBC count, WBC count with differential (neutrophils [count and percent] and lymphocytes, monocytes, eosinophils, basophils [percent]), and platelet count.
- Serum chemistries (non-fasting), blood urea nitrogen (BUN; urea is acceptable for countries where BUN is not tested), total cholesterol, creatinine, glucose, lactate dehydrogenase (LDH), sodium, potassium, calcium, chloride, bicarbonate, magnesium, phosphorus, albumin, and total protein.
- LFTs, including ALT, AST, alkaline phosphatase, and total and direct bilirubin.
- Thyroid panel, including thyroid-stimulating hormone (TSH), free triiodothyronine (T3), and free thyroxine (T4).
- Urinalysis, including color, appearance, specific gravity, pH, glucose, bilirubin, ketones, occult blood, protein, leukocytes, nitrites, and urobilinogen.

- Calcitonin, CEA: for patients with MTC only. For each patient, all tests for calcitonin and CEA should be performed in the same laboratory to minimize intra-patient, lab-to-lab variability in their measurement.
- Thyroglobulin: for patients with non-MTC thyroid cancers only (unless not measurable due to presence of anti-thyroglobulin antibodies). For each patient, all tests for thyroglobulin should be performed in the same laboratory to minimize intra-patient, lab-to-lab variability in their measurement.
- Serum cortisol, Serum ACTH, 24-hour urine for free cortisol: optional for patients with Cushing's disease related to their cancer.
- Participants under age 18 who have not yet obtained full adult height should undergo radiograph of one knee at baseline for growth plate assessment.
- Whole blood for genomic DNA: obtained any time within 28 days prior to treatment on C1D1.
- Baseline disease assessment with radiographic tumor measurements using:
  - All patients: computerized tomography (CT) or magnetic resonance imaging (MRI) of chest, abdomen, and pelvis, and any other areas with suspected disease involvement, within 28 days of C1D1.
  - All fusion-positive solid tumor patients, patients with a history of CNS metastases, or other patients if clinically indicated: brain imaging, MRI with and without contrast is preferred, CT with and without contrast is acceptable if MRI is medically contraindicated, within 28 days of C1D1.
  - For each modality, intravenous (IV) and oral contrast should be utilized (chest CT does not require IV contrast) where applicable unless medically contraindicated.
  - If CT/positron emission tomography (PET) is utilized, the CT component of CT/PET must be of the same quality as a dedicated diagnostic CT scan, i.e., with IV and oral contrast and 5 mm or less slice thickness.

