**Notes:**

- Patients who do not have adequate archival tumor tissue available (refer to specific archival tissue requirements in Section 7.8.5.1) should undergo a fresh tumor biopsy, if it is considered safe to perform, prior to treatment (requirement may be waived with Sponsor approval).
  - If archived tumor tissue was obtained prior to progression on the last MKI with anti-RET activity, the patient should undergo a fresh tumor biopsy, if it is considered safe to perform prior to treatment (optional).
9. Adequate hematologic status, defined as:
    - Absolute neutrophil count (ANC)  $\geq 1.0 \times 10^9/\text{L}$  not requiring growth factor support for at least 7 days prior to treatment, and
    - Platelet count  $\geq 75 \times 10^9/\text{L}$  not requiring transfusion support for at least 7 days prior to treatment, and
    - Hb  $\geq 9$  g/dL not requiring transfusion support or erythropoietin for at least 7 days prior to treatment.
  10. Adequate hepatic function, defined as:

ALT and AST  $\leq 2.5 \times$  the upper limit of normal (ULN) or  $\leq 5 \times$  ULN with documented liver involvement (such as liver metastasis or a primary biliary tumor); and

Total bilirubin  $\leq 1.5 \times$  ULN or  $\leq 3 \times$  ULN with documented liver involvement (patients with Gilbert's Disease may be enrolled with prior Sponsor approval).

11. Adequate renal function, with estimated glomerular filtration rate  $\geq 30$  mL/minute (up to 6 patients with an estimated glomerular filtration rate [eGFR]  $\geq 15$  and  $< 30$  mL/minute will be allowed to enroll with Sponsor approval).
12. Ability to swallow capsules and comply with outpatient treatment, laboratory monitoring, and required clinic visits for the duration of study participation.
13. Willingness of men and women of reproductive potential to observe conventional and effective birth control for the duration of treatment and for 1 month following the last dose of study treatment.

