**Notes:**

- A postmenopausal woman will be defined as having no menses for 12 months without an alternative medical cause. Male sterility will be defined as only men sterilized surgically. For male patients with a pregnant partner, a condom should be used for contraception. For male patients with a non-pregnant female partner of child-bearing potential and woman of child-bearing potential one of the following birth control methods with a failure rate of less than 1% per year when used consistently and correctly are recommended:
  - a. Combined estrogen and progesterone containing hormonal contraception associated with inhibition of ovulation given orally, intravaginally, or transdermally
  - b. Progesterone-only hormonal contraception associated with inhibition of ovulation given orally, by injection, or by implant
  - c. Intrauterine device (IUD)
  - d. Intrauterine hormone-releasing system (IUS)
  - e. Bilateral tubal occlusion
  - f. Vasectomized partner
  - g. Sexual abstinence
    - Sexual abstinence is considered a highly effective method only if defined as refraining from heterosexual intercourse during the entire period of risk associated with the study treatments. The reliability of sexual abstinence needs to be evaluated in relation to the duration of the clinical trial and the preferred and usual lifestyle of the subject.
- Birth control methods unacceptable for this clinical trial are:
  - a. Periodic abstinence (calendar, symptothermal, or post-ovulation methods)
  - b. Withdrawal (coitus interruptus)
  - c. Spermicide only
  - d. Lactational amenorrhea method

Male study participants should refrain from sperm donation during study treatment and up to 6 months following the last dose of selpercatinib.

Women of childbearing potential is a woman who is fertile, following menarche and until becoming post-menopausal unless permanently sterile. Permanent sterilization methods include hysterectomy, bilateral salpingectomy and bilateral oophorectomy.

A man is considered fertile after puberty unless permanently sterile by bilateral orchidectomy.

## 4.2 Inclusion Criteria for Phase 2

Inclusion Criteria are the same as for Phase 1, with the following modifications:

1. Cohorts 1 and 3: failed or intolerant to standard of care; Cohorts 2 and 4: without prior standard-first line therapy. See [Table 4-1](#) for examples.

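### The pregnancy-test waiver ignores why menses are absent, so a fertile woman with medically caused amenorrhea is of childbearing potential under Section 4.1 but need not be tested

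*Protocol*

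**What the plan says.** Sections 7.1, 7.2 (Day 1), 7.3, 7.5 and 7.6 and Table 7-1 footnote l each order a pregnancy test for women of childbearing potential. Each then adds a parenthesis saying that "surgically sterilized females or those who have not experienced menses for at least 2 years are not required to be tested". Together these places cover screening, Day 1 of every cycle, the End of Treatment (EOT) visit and the Safety Follow-Up (SFU) visit.

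The terms are defined in the notes to inclusion criterion 13 in Section 4.1:

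- A postmenopausal woman is one "having no menses for 12 months without an alternative medical cause".
- A woman of childbearing potential is one who is fertile, "following menarche and until becoming post-menopausal unless permanently sterile".
- On sterility: "Permanent sterilization methods include hysterectomy, bilateral salpingectomy and bilateral oophorectomy". Absence of menses is not on that list.

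Pregnancy is an exclusion (Section 4.3, criterion 13) and a reason for removal from treatment (Section 6.4). Section 9.6 requires immediate withdrawal of a patient who becomes pregnant on study drug.

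**The concern.** The waiver and the definition use different tests for the same question. Section 4.1 asks how long menses have been absent and why. The waiver asks only how long. Its interval is longer (two years against 12 months), but a longer interval does not replace the condition on cause, which is what separates menopause from amenorrhea with some other explanation.

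Scheduled testing is the protocol's systematic means of finding an unrecognized pregnancy before the first dose or during treatment. For the women caught between the two texts, that means becomes optional at every visit. What is at stake is possible exposure of a pregnancy to study drug. No estimate of response, duration of response or survival depends on it.

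**Working it through.** The plan gives no figure to reproduce. The check is a comparison of texts, followed by a count of the tests involved.

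**Comparison.** Take a fertile woman, not permanently sterile, without menses for at least two years because of a medical cause other than menopause.

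1. Postmenopausal under Section 4.1? No. The definition requires that there be no alternative medical cause.
2. Permanently sterile under Section 4.1? No, by assumption.
3. Of childbearing potential under Section 4.1? Yes. She is past menarche, fertile, not postmenopausal and not permanently sterile.
4. Covered by the waiver? Yes. It asks only for two years without menses.
5. Does any other text supply the missing condition? No. All six places carry the waiver without it.

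The same woman is therefore inside the class to be tested and inside the class that need not be tested.

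**Tests not required per affected woman.** For a woman who stops after *k* cycles of 28 days, the schedule asks for screening (1) + Day 1 visits (*k*) + EOT (1) + SFU (1) = *k* + 3. Subtract 1 if screening within 48 hours of first dose serves as Cycle 1 Day 1 (Section 7.1), and 1 if SFU is combined with EOT (Section 7.6). The lower count is then *k* + 1.

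| Cycles | Days | Tests |
|---|---|---|
| 6 | 168 | 7 to 9 |
| 13 | 364 | 14 to 16 |
| 26 | 728 | 27 to 29 |

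After two years on treatment, cycles lengthen to 84 days (Table 7-1, asterisk footnote). Day 1 visits then fall from 365.25/28 = 13.0 to 365.25/84 = 4.3 a year. Three years is 3 × 365.25 ≈ 1,096 days.

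- If the change follows 26 short cycles, further Day 1 visits fall on days 729, 813, 897, 981 and 1,065. That makes 26 + 5 = 31 visits and 32 to 34 tests.
- If it follows 27 short cycles, they fall on days 757, 841, 925, 1,009 and 1,093. That makes 27 + 5 = 32 visits and 33 to 35 tests.

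The three-year range is 32 to 35. These counts describe the schedule and do not measure harm.

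**The case against.** The strongest reply is that the operative rule already covers these women. Each place orders a test for women of childbearing potential, Section 4.1 defines that term, and the parenthesis can be read as shorthand for women outside it. A site applying Section 4.1 strictly would test the affected woman. That is a fair reading, and it means the text does not forbid testing. It does not remove the conflict: as shorthand, the parenthesis describes the excluded class wrongly, and it still says that these women need not be tested.

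Other points on that side stand:

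- Contraception still applies. Under criterion 13, patients of either sex who are able to have children must "observe conventional and effective birth control for the duration of treatment and for 1 month following the last dose of study treatment".
- The documents identify no affected patients. One example, which is an assumption from general clinical knowledge, is a woman without menses on a hormone-releasing intrauterine system. It is a weak one, since Section 4.1 lists that device among methods with a failure rate below 1% per year. The textual conflict does not depend on it.
- Few patients may be reached. Appendix M (Amendment 11) records a decision to end enrollment to most populations. SAP Section 2.1 describes enrollment as still ongoing only for *RET* fusion-positive cancers other than NSCLC and thyroid. Table 7-2 lists no pregnancy test in continued access.

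A reader might infer from Section 4.1's rejection of the "Lactational amenorrhea method" that the protocol knowingly exposes women with amenorrhea. The documents do not support that. The list concerns acceptable contraception, not who is tested, and lactating women are excluded in any case. A reader might also infer that the words on surgical sterilization are a defect of the same kind. Nothing here shows that. Section 4.1 lists bilateral tubal occlusion as a birth control method, separately from permanent sterilization, so replacing those words with a reference to its sterility definition would put the status of women with tubal occlusion in doubt.

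**Conclusion.** The inconsistency is real and minor. A fertile woman with two or more years of medically caused amenorrhea is of childbearing potential under Section 4.1 and is not required to be tested at any scheduled visit. This rests on the wording of Section 4.1 and of the six schedule texts, and on no clinical estimate.

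The stronger reading, that pregnancies will be missed or that these women are unprotected, is not supported. The documents give neither the number of women affected nor any probability of an undetected pregnancy. Testing remains permitted, and the contraception requirement and the pregnancy exclusion still bind. The number affected is assumed to be small. A correction at screening reaches only remaining enrollment. On treatment it reaches only ongoing patients not yet in continued access. The efficacy analyses do not change.

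**What to change.** In Sections 7.1, 7.2, 7.3, 7.5 and 7.6 and Table 7-1 footnote l, insert *without an alternative medical cause* directly after the two-year interval in the parenthesis. Leave the reference to surgically sterilized females unchanged. Keep the two-year interval, so that women 12 to 24 months without menses whom sites now test do not drop out of testing.

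The cost is one phrase in six places at the next amendment, and a few extra urine or serum tests for a probably small number of women at visits already scheduled. From Cycle 7, Section 7.3 allows these tests at a local facility in cycles without disease assessment, though Appendix K removes the local-facility option in Germany. The protocol does not define an alternative medical cause, so sites will have to decide that clinically, as Section 4.1 already asks them to.
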